A post-baccalaureate study coordinator with a background in psychology or a related field will perform many important tasks for the U01 project. After appropriate training, the study coordinator will conduct the bulk of the initial telephone screening interviews. He/she will also conduct diagnostic interviews at baseline and one-month and three-month follow-up assessments and track attendance at scheduled dental appointments for the 12-month period following the dental anxiety intervention. He/she will also complete reliability ratings for diagnostic interviews conducted by other study staff, providing full coverage of this activity with the graduate student. The study coordinator will also be charged with the rating of treatment fidelity/adherence of a portion of the

Page 6 of 28 Revision: May 12, 2023

interventions completed during the U01 project. The study coordinator will also conduct a range of data entry and management activities.

The dental staff for the proposed U01 will be two or more part-time dental assistants or expanded function dental assistants as defined in the State of Pennsylvania working with [name] at TUKSoD (one full-time equivalent). They will be trained in the administration of the Internet-based dental anxiety intervention by a psychologist, postdoctoral fellow, or doctoral student highly trained in CBT and the specific online intervention, and they will administer the dental anxiety intervention to those patients randomly assigned to the arm of the trial in which the intervention is delivered by dental staff. They will also assist in the payment of study subjects and other day-to-day tasks when these activities cannot be performed by the post-baccalaureate study coordinator.

7) Prior Approvals

See attached letters of support from the Directors of the Faculty Practice Clinic and the Graduate Clinics of TUKSoD.

8) Study Design

a) Recruitment Methods

Approximately 550 patients will participate in this research, roughly evenly divided between the three arms of the study.

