Pain Intensity Numeric Rating Scale (PI-NRS). The PI-NRS is a widely utilized 11-point measure that assesses physical pain intensity on a scale ranging from 0 (no pain) to 10 (worst possible pain). The PI-NRS has been used to assess pain intensity in several studies conducted in medical settings (Farrar et al., 2001, 2010; Rowbotham et al., 2004; van der Roer, 2006). Anxiety increases subjective pain experience, and therefore this scale will be used to assess the intensity of dental related pain that participants experienced during their scheduled dental appointment and expect to experience at their next dental appointment. The PI-NRS will be administered as part of the post-dental-appointment debriefing interview.

Attendance at Dental Appointments

Given that avoidance of dental appointments is strongly connected to dental anxiety, we will also assess whether the Internet-based dental anxiety intervention increases attendance at future dental appointments. We will utilize TUKSoD's automated scheduling system (axiUm, http://www.axiumdental.com/) to do so. It is acknowledged that attendance may be influenced by factors unrelated to dental anxiety, but it is a reasonable hypothesis that anxious avoidance plays a role in attendance, and individuals with dental phobia are less likely to visit a dentist at least once a year than persons without. Thus, it is of interest to determine whether attendance at appointments scheduled prospectively after the index appointment is affected by treatment, and we will monitor this for the following 12-month interval. These data will not be collected for active control patients, who will be offered the intervention to be administered before their first scheduled dental appointment after the completion of the 3-month follow-up.

Planned Analyses

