Aim 1 will test the equivalence hypothesis (Ho: the two intervention conditions are not equivalent). MDAS and ADIS fear scores will be the primary outcomes to be compared between two intervention conditions for equivalence. The two one-sided tests (TOST) procedure of Schuirmann (1987) will be used to conduct the equivalence test. Linear mixed-effects models for repeated measures will be used to assess differences between intervention groups using the MDAS and ADIS fear rating as continuous outcome variables. Linear mixed-effects models will also investigate the treatment effect on dental anxiety or fear after accounting for other confounding factors. Similar analyses will be conducted for secondary outcome measures (pain sensitivity index, anxiety sensitivity index, sleep disturbance and sleep-related impairment scales, disability scale, distress tolerance scale, client satisfaction and blood-injury-injection phobia). Statistical significance will be set at p < 0.05. Multiple imputation (MI) will be used to handle missing follow-up data as described below.

Aim 1 will also determine whether the Internet-based intervention reduces dental anxiety/fear as determined by self-ratings or assessor ratings at one month and three months post-intervention. Initially, we will assess within-group change of anxiety or fear scores for each condition separately using paired *t*-tests. Linear mixed-effects models will be used to estimate within-group reduction of anxiety/fear at assessments one and three months after the administration of the intervention adjusting for other covariates.

Specific Aim 2

Aim 2 will assess the superiority hypothesis (Ho: there are no significant differences between the interventions and control). MDAS and ADIS-5 fear scores will be the primary outcomes to be compared. Initially, we will assess the differences between the interventions and control using two-sample *t*-tests. The main analysis will be based on linear mixed-effects models for repeated measures (using the MDAS score and ADIS-5 fear rating as continuous outcome variables) to assess differences between intervention and control groups. Linear mixed models will also investigate the treatment effect on dental anxiety or fear after accounting for other confounding factors. Similar analyses will be conducted for secondary outcome measures (e.g., client satisfaction and blood-

Page 17 of 28 Revision: May 12, 2023

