injury-injection phobia). Statistical significance will be set at p < .05. MI will be used to handle missing follow-up data as described below.

Specific Aim 3

Aim 3 examines the impact of the intervention on attendance at scheduled dental appointments over the following 12-month period to determine whether the intervention affects avoidance of dental procedures. First, we will examine whether the overall attendance rate is changed from pre- to post-intervention using a one-sample Chisquare test comparing the 12-month periods immediately before and immediately after the delivery of the intervention. The two intervention groups combined will be used for this analysis. We will also use a Chi-square test to compare post-intervention attendance rates between the two intervention groups. We expect the attendance rates will be similar for the two groups. Finally, we will conduct logistic regression analyses predicting attendance/nonattendance among intervention patients who did or did not demonstrate reduction in dental anxiety at 3-month follow-up. Relevant demographic characteristics and other potential confounding variables or moderators will be included in the final logistic models.

Missing Data

MI will be used to handle missing follow-up data when conducting ITT analysis for Specific Aims 1 and 2. There will be three steps in the MI procedure: 1) The missing follow-up data will be filled in 100 times to generate 100 complete datasets; 2) The 100 datasets will be analyzed by analyses of covariance with follow up scores at 1-month or 3-month as outcomes and treatment groups as the independent variable (Tr1 vs. Tr2 for Specific Aim 1, or Tr1 + Tr2 vs. AC for Specific Aim 2), controlling for baseline scores; 3) The results from the 100 complete datasets will be combined for the MI inference (Rubin 1987). SAS PROC MI and PROC MIANALYZE will be used for multiple imputation analysis using SAS 9.4 (SAS Institute Inc., Cary, NC, USA).

Analysis of Secondary Objectives

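### Aim 3 expects similar attendance in the two I-CBT arms, but the only between-arm analysis it names is a chi-square test of difference, which cannot support similarity

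*Combined protocol and SAP*

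**What the plan says.** Attendance over 12 months is Objective 3, one of three primary objectives in section 4. In section 8c, Planned Analyses, Specific Aim 3 sets out three analyses:

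- A before-and-after comparison with the two I-CBT arms pooled: "First, we will examine whether the overall attendance rate is changed from pre- to post-intervention using a one-sample Chisquare test".
- The between-arm comparison at issue: "We will also use a Chi-square test to compare post-intervention attendance rates between the two intervention groups". The sentence that follows it is "We expect the attendance rates will be similar for the two groups".
- Logistic regression of attendance among I-CBT patients who did or did not show reduced dental anxiety at 3 months. This is not a comparison of the arms.

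Control patients contribute nothing here. The section on attendance at dental appointments says of these data: "These data will not be collected for active control patients".

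For the same two arms, Specific Aim 1 states a null of non-equivalence and says "The two one-sided tests (TOST) procedure of Schuirmann (1987) will be used to conduct the equivalence test". It applies this to MDAS and ADIS-5 fear and carries similar analyses over to a list of secondary scales. Attendance is not on that list. The section on secondary objectives reuses the methods for objectives 1 and 2 only.

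**The concern.** The chi-square test takes equal rates as its null. A significant result would contradict the stated expectation. A non-significant result is compatible with it, but equally compatible with any gap the data are too few to exclude, and it becomes more likely as the data become less informative. So no result of the named test can count as evidence for what the plan expects, and Aim 3 supplies no margin, interval or decision rule that could.

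The comparison between I-CBT arms is the only randomised comparison in Aim 3, because the other two analyses are before-and-after or conditional on anxiety response. If the report gave only a chi-square p-value beside the stated expectation, a reader could take p > 0.05 as showing that delivery by dental assistants makes no difference to attendance.

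**Working it through.** **No figure to reproduce.** The documents give no attendance rate, margin, power or sample-size calculation for Aim 3.

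**Inputs from the documents**
- Size: "Approximately 550 patients will participate in this research, roughly evenly divided between the three arms of the study" (section 8a). 550/3 gives about 183 per I-CBT arm.
- Significance level: "Statistical significance will be set at p < .05" is stated under Aim 2, and the same level under Aim 1. It is not repeated for Aim 3.

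**Assumptions**
- Two-sided 0.05; one attended/not-attended status per patient.
- Attendance rates from 50% to 95%, shown as a range.
- A 10-point gap as benchmark.
- Loss of attendance data of 0% or 15% (0.85 × 183 ≈ 156 per arm).

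**Step 1: chance that a true 10-point gap is non-significant.** With mean rate p̄ and gap d = 0.10:

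SE0 = √[2p̄(1−p̄)/n]; SE1 = √{[p1(1−p1) + p2(1−p2)]/n}; P(non-significant) = 1 − Φ[(d − 1.96·SE0)/SE1].

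For 70% versus 60%, n = 183: SE0 = √(2 × 0.65 × 0.35/183) = 0.0499; SE1 = √[(0.21 + 0.24)/183] = 0.0496; (0.10 − 0.0977)/0.0496 = 0.046; Φ = 0.518; P(non-significant) = 48%.

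| True rates | Non-significant, 183 per arm | Non-significant, 156 per arm | p if a 10-point gap is observed, 183 per arm |
|---|---|---|---|
| 95 vs 85 | 11% | 16% | 0.001 |
| 90 vs 80 | 23% | 30% | 0.007 |
| 80 vs 70 | 40% | 47% | 0.027 |
| 70 vs 60 | 48% | 54% | 0.045 |
| 60 vs 50 | 51% | 57% | 0.055 |

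Simulation with 400,000 draws, run for all rows but the first, agreed within about 1 point. The last column uses z = 0.10/SE0 and shows why the gap must be described as true, not observed.

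**Step 2: what a confidence interval would show.** The 95% half-width at a common rate p is 1.96·√[2p(1−p)/183]. At p = 0.70 this is 1.96 × √(0.42/183) = 0.094. It is 6.1 points at 90%, 8.2 at 80%, 9.4 at 70%, 10.0 at 60% and 10.2 at 50%.

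**Step 3: what TOST could deliver.** With true difference 0, one-sided 0.05 and margin m, power = 2Φ(m/SE − 1.645) − 1, where SE = √[2p(1−p)/183]. At p = 0.70 and m = 0.10, SE = 0.0479, m/SE − 1.645 = 0.442, and power = 34%.

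| Common rate | Power, m = 10 points | n per arm for 80% power, m = 10 | Power, m = 15 points |
|---|---|---|---|
| 90% | 88% | 155 | 99.8% |
| 80% | 55% | 275 | 95% |
| 70% | 34% | 360 | 86% |
| 60% | 24% | 412 | 80% |
| 50% | 21% | 429 | 78% |

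Both margins are illustrations; neither comes from the documents.

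**The case against.** The strongest reply is that the plan draws no wrong conclusion. A reader might infer that p > 0.05 will be declared similarity, but no sentence says so; Aim 3 records an expectation beside a test. Where the authors want a formal equivalence hypothesis they write one, as in Aim 1, and Objective 3 does not mention provider comparability. A difference test as a between-arm check is legitimate if it is not over-read. All of this stands. What remains is that Aim 3 contains nothing that could support its own expectation.

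A reader might also infer that an observed 10-point gap would slip through. At 183 per arm it would usually be significant, as the table shows; it would not be at rates near 50–60%, or at somewhat higher rates after attrition.

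Nor do the documents rest the dissemination argument on attendance. The abstract ties dissemination to relative equivalence of efficacy, describes efficacy through anxiety and fear measures plus secondary measures, and lists attendance separately. The attendance section itself accepts that attendance may reflect things other than dental anxiety.

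Finally, the numbers depend on assumed rates, and at very high attendance the chance of missing a true 10-point gap is small. That is why a range is given. The logical point holds at any rate.

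**Conclusion.** The concern holds in a limited form. The only between-arm attendance analysis named in Aim 3 tests for a difference, while the stated expectation is similarity, and no margin, interval or rule connects the two. Under the assumptions above, a true 10-point gap would be non-significant between about 11% and 51% of the time at 183 per arm, depending on the attendance rate, and between 16% and 57% with 15% loss.

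The documents do not say whether the unit is the patient or the appointment. Per-appointment data would be clustered within patients and would change all these figures; the net direction cannot be worked out from what is given. The point concerns one analysis within a primary objective and does not touch the MDAS or ADIS-5 fear analyses.

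**What to change.** Amend Specific Aim 3 as follows:

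- Make the between-arm difference in attendance, with its 95% CI, the main between-arm result. The chi-square p-value may be reported beside it.
- State that a non-significant chi-square will not be read as similar attendance.
- Say whether the unit is the patient or the appointment; if the latter, use an interval that allows for repeated appointments in the same patient.
- Optionally, if a margin can be justified and fixed without sight of attendance data by arm, judge similarity by TOST, that is, by whether the 90% CI lies within the margin. Aim 1 states no margin to borrow. This revision is dated May 12, 2023 and the hoped-for completion date is July 31, 2023, so blindness to attendance by arm would need to be documented. Without such a margin, report the difference and interval and draw no conclusion of similarity.

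The cost is wording only: no new data, visits or patients. The downside is that the interval may be too wide to support similarity unless attendance is high or the margin is wide. For an illustrative 10-point margin, TOST power is 21% to 88% at common rates of 50% to 90%.

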basic training in the nature and use of cognitive coping skills. (3) The third video was filmed from the perspective of a patient in the dental chair and provides additional and more intensive exposure to the feared dental procedure. The voiceover is a "dialogue" between the acting patient in the video, who presents cognitive coping from a self-administered/self-help perspective, and the participating patient, who is led through the steps to develop coping thoughts to counter his/her own anxious thoughts. The intervention closes with a brief module providing additional motivational enhancement for attending future dental appointments. Upon completing the intervention, patients attend their scheduled dental appointment and are encouraged to use the skills they learned from the intervention to cope with any anxiety they experience during that appointment.

The computer-based intervention was piloted on a sample of six dental patients from the TUKSoD Clinics (Potter et al., 2016). All patients completed the experimental intervention and attended their appointment for dental care, and 5/6 were contacted and re-assessed after one month. Three patients demonstrated clinically significant reductions in dental anxiety, and the remainder demonstrated lesser improvements. We next conducted a randomized controlled trial of the experimental intervention in comparison to a waitlist control condition (N = 151; Tellez et al., 2015). The computer-based intervention resulted in greater declines in dental anxiety, and clinician ratings of dental fear and avoidance were also markedly reduced. Among those who met criteria for dental phobia at baseline, a larger percentage of treated patients no longer did so after the treatment interval than was the case for patients assigned to the waitlist condition. Patients who received this computerized dental anxiety intervention reported high levels of satisfaction (83% were "very satisfied").

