To assist in recruitment and retention, we will focus on strategies that we utilized in our recently completed randomized controlled trial for the computer-based version of the intervention and others that we believe to be useful based on that experience with the same patient population. These will include reminder calls and text messages the week before, the day before, and the day of appointments as well as patient payments for completion of assessments (\$75 for completion of screening/baseline assessments and initiation of the in-clinic visit, \$50 for completing each of the follow-up assessments). We will coordinate closely with the front office staff of the Faculty Practice Clinic in assuring that we are fully aware of patient-initiated schedule changes and to minimize the likelihood that the dental treatment appointment will not be pushed back or rescheduled by the dental treatment staff without advance notice (an issue that arose at times in the conduct of the trial of the computer-based version of the intervention).

Inclusion and Exclusion Criteria

Inclusion criteria will require that the patient endorse high dental anxiety (a total score of 19 or a score of 4-5 on at least 2 of the 5 items) on the Modified Dental Anxiety Scale (Humphris et al., 1995), endorse at least mild impairment as a result of that anxiety at the screening interview, be between 18 and 75 years of age, and be sufficiently fluent in

Page 8 of 28 Revision: May 12, 2023

written and spoken English in the judgment of project staff that the patient would be able to benefit from the intervention and validly complete the assessments.

Exclusion criteria are the following: (a) a self-reported currently uncontrolled medical condition (e.g., heart attack, seizure disorder) that might make exposure to anxiety-evoking stimuli inadvisable; or (b) inability to give informed consent. Participants will not be excluded on the basis of gender, ethnicity/race, or other demographic characteristics, nor will they be required to meet criteria for a formal diagnosis of dental phobia.

b) Study Timelines

- This clinical trial will last for a period of 5 years
- The first 6 months will be devoted to recruitment and training of staff.
- Patient recruitment is estimated to take up to 45 months, with the final enrollee completing follow-ups 3 months later (and monitoring of their attendance at dental appointments continuing for 9 additional months).

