Modified Dental Anxiety Scale (MDAS; Humphris et al., 1995). The MDAS is a widely used 5-item measure assessing fear of dental procedures, including cleaning, drilling, and local anesthetic injections; for example, "If you were about to have your tooth drilled, how would you feel?" Items are rated on a 5-point Likert-type scale ranging from 1 (not anxious) to 5 (extremely anxious). The total score ranges from 5 to 25; a score of 19 or above indicates high anxiety based on receiver operating characteristic analyses from two studies. The MDAS has demonstrated good internal consistency (α = .89 in Humphries et al., 1995; α = .91 in our pilot work) and test-retest reliability (r = .82). The MDAS will be administered at several occasions throughout the study. We will also briefly contact patients and ask them to complete the MDAS by phone or online at 6-month and 12-month follow-ups as well.

Medical Screening Interview. During the initial telephone screening, we will administer a medical screening interview that has been used in previous research by former PI [name] at Temple University. This medical screening interview assesses a number of medical conditions that may make it inadvisable for the potential participant to be exposed to anxiety-evoking materials unless well-controlled. If the potential participant meets criteria for any of these medical conditions and does not report that they are controlled by medication or other appropriate means, that potential participant will be excluded. It is also important to note that the Faculty Practice Clinic (the clinic in which the trial will be conducted) also conducts it own medical screening and will not schedule a patient for an appointment for dental care if the patient scores positive for any of the listed conditions on their form unless it is medically controlled (patient will be first referred out for appropriate medical care before coming back to the dental clinic when the medical condition is controlled). Although the routine clinical procedures of Faculty Practice Clinic are not a formal part of our protocol, they are thorough and suggest that our procedures are conservative, as we are recruiting only from the population of patients for whom an appointment for dental care has already been scheduled.

Other Self-Report Questionnaires

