We propose general statistical analyses and sample size considerations for the U01 trial. Initial analyses will be conducted to determine normality of distributions of the continuous variables, and any necessary transformations will be conducted. Primary outcomes will be the MDAS (score ranging from 5 to 25) and the rating of fear of dental procedures from the ADIS-5 (0=no fear to 8=very severe fear). All eligible patients will be randomly assigned to one of the three conditions described above. Although randomization should provide relatively comparable groups, demographic variables that differ between groups and are correlated with the primary outcomes will be used as covariates. Patients will receive a full battery assessment of outcome measures at baseline and 1 and 3 months after the day of their index dental appointment (as well as assessments on the day of their index dental appointment).

Page 16 of 28 Revision: May 12, 2023

Preliminary statistical analysis will include measures of central tendency and dispersion, as well as an examination of the bivariate relationships among the primary and secondary outcome variables (e.g., client satisfaction, blood-injury-injection phobia), potential moderators (e.g., distress tolerance and pain sensitivity), and demographic characteristics.

Differences between the groups on baseline demographic, clinical and psychological measures will be examined using χ^2 (Pearson) or Student's *t*-tests, as appropriate. Moreover, differences on the variables listed above among completers and drop-outs will also be explored. Both per protocol and intention to treat (ITT) analyses will then be conducted.

Specific Aim 1

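### Aim 3 relates attendance to an undefined yes/no reduction in anxiety at 3 months, which discards at least about 36% of the information in the change score

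*Combined protocol and SAP*

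**What the plan says.** Section 8(c), Planned Analyses, Specific Aim 3, lists three analyses of 12-month attendance. The first is a before/after comparison in the pooled intervention arms and the second compares the two intervention arms. The third is logistic regression "predicting attendance/nonattendance among intervention patients who did or did not demonstrate reduction in dental anxiety at 3-month follow-up". Demographic characteristics and other possible confounders or moderators are to enter the final models, but none is named. Controls contribute nothing to Aim 3; section 8(c), Attendance at Dental Appointments, states "These data will not be collected for active control patients".

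Aim 3 does not say what a reduction is. Three elements are open:

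- **Instrument.** The general text under Planned Analyses names two candidates: "Primary outcomes will be the MDAS (score ranging from 5 to 25) and the rating of fear of dental procedures from the ADIS-5".
- **Reference score.** Table 1 schedules the MDAS at both screening and baseline.
- **Minimum size.** None is given.

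Table 1 also shows that the MDAS and the ADIS-5 module are both collected at baseline and at 3 months. Aims 1 and 2 model the MDAS and ADIS-5 fear scores as continuous.

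**The concern.** Attendance over 12 months is one of the three primary objectives, and this regression is the only planned analysis that links change in anxiety to attendance. It reduces a graded score to two classes and gives no reason for doing so.

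Two consequences follow. First, a two-class predictor carries less information than the score it came from, so a real association is more likely to be missed. Second, because the class is undefined, the cut could be chosen after the attendance data have been seen. On the most literal reading it would also place many unchanged patients among the improved. A weak or null result could then reflect the grouping and be reported as evidence that reducing anxiety does not affect attendance.

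**Working it through.** The plan gives no power, responder rate or misclassification rate for Aim 3, so there is no stated figure to reproduce.

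**Inputs from the documents**

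- Sample: "Approximately 550 patients will participate in this research, roughly evenly divided between the three arms of the study". Two of three arms give 550 × 2/3 ≈ 367. Applying the earlier trial's one-month loss of 2 in 46 (section 8(d)) gives 367 × (1 − 2/46) ≈ 351 at 3 months.
- MDAS "test-retest reliability (r = .82"), with the retest interval not stated.
- MDAS steps: "Items are rated on a 5-point Likert-type scale ranging from 1 (not anxious) to 5 (extremely anxious"). There are five items, so the total moves in whole points.
- Entry rule at screening: "a total score of 19 or a score of 4-5 on at least 2 of the 5 items".

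**Assumed, because the documents do not give them:** MDAS SD 2-5; mean fall 1-6 points; SD of change 2.5-5; one yes/no attendance outcome per patient with 60-80% attending; odds ratio 1.3-1.5 per SD of change; two-sided alpha 0.05.

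**1. Information kept by a split.** For a normal predictor cut so that a proportion p lies on one side, the share kept is φ(z_p)² / [p(1 − p)].

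| Split | Kept | Lost |
|---|---|---|
| 50/50 | 0.3989² / 0.25 = 0.64 | 36% |
| 70/30 | 0.58 | 42% |
| 80/20 | 0.2800² / 0.16 = 0.49 | 51% |
| 90/10 | 0.1755² / 0.09 = 0.34 | 66% |

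The 50/50 split is the best case, so the loss is at least about 36% wherever the cut falls.

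**2. Unchanged patients classed as improved, if any MDAS fall from baseline counts.** The SD of the difference between two scores with no true change is SD × √[2(1 − 0.82)] = 0.6 × SD. With whole-point scores, the chance of a fall of at least 1 point is Φ[−0.5 / (0.6 × SD)]. The 95% reliable-change value is 1.96 × 0.6 × SD.

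| Assumed SD | SD of difference | Chance of a fall | Reliable change |
|---|---|---|---|
| 2 | 1.2 | 34% | 2.4 points |
| 3 | 1.8 | 39% | 3.5 points |
| 4 | 2.4 | 42% | 4.7 points |
| 5 | 3.0 | 43% | 5.9 points |

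A simulation with rounding, limits of 5 and 25, and entry at a screening score of 19 or more gives 36-43% when change is measured from baseline. Measured from the screening score it gives 42-64%, because patients selected on a high score tend to score lower next time. For ADIS-5 fear, assuming SD 1-2 and borrowing r = .82, the formula gives 20-34%. The undefined instrument and reference score therefore matter to the answer.

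**3. Number of non-responders under the same rule.** The share with no fall is 1 − Φ[(mean fall − 0.5) / SD of change], applied to 351 patients with SD of change 2.5-5.

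| Mean fall | Share with no fall | Patients |
|---|---|---|
| 1 | 42-46% | 148-161 |
| 2 | 27-38% | 96-134 |
| 3 | 16-31% | 56-108 |
| 4 | 8-24% | 28-85 |
| 5 | 4-18% | 13-65 |
| 6 | 1-14% | 5-48 |

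The range is too wide to say whether the group would be small.

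**4. Illustrative power.** At odds ratio 1.4 per SD, 70% attendance and n = 351, the continuous predictor has about 80% power. A split has 62% at 50/50, 60% with 30% non-responders, 55% with 20% and 44% with 10%. Over the full assumed ranges, power is 49-94% for the continuous predictor and 26-83% for the split.

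**The case against.** The strongest objection is that the plan never adopts an any-fall rule. A reader might infer one from the wording, but it is only the literal reading. Section 5 separates larger from smaller gains in the pilot, and section 8(c) sets a clinical-significance level on the ADIS-5 severity rating, so a threshold may have been intended. This stands: what the documents show is an undefined term, and the 34-43% is conditional on one reading of it. It also applies only to patients with no true change, whose number is unknown.

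A reader might also infer that few non-responders would remain, since the pilot reports "Three patients demonstrated clinically significant reductions in dental anxiety, and the remainder demonstrated lesser improvements". The documents do not support that. The pilot had six patients, five re-assessed at one month, on the computer-based version, and the measure behind the lesser improvements is not stated. Step 3 shows that the group size turns on a mean change and SD that are not given.

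Nor do all the effects bias the result towards no association. A small group widens the confidence interval, and ignoring the size of improvement costs power and changes the question. Of these, only misclassification attenuates. Imperfect reliability would attenuate a continuous change score too, so it does not count against the split alone.

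Finally, the other two Aim 3 analyses do not use the split, this one is a non-randomised association among treated patients, and baseline adjustment is already possible under the confounder wording. That limits the reach of the point. It does not supply a definition of reduction or restore the lost information.

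**Conclusion.** The point holds as an undefined responder term combined with avoidable dichotomisation. The loss of at least about 36% of the information needs only a roughly normal change score and does not depend on where the cut falls; it is larger for uneven splits (51% at 80/20, 66% at 90/10). The 34-43% misclassification of unchanged patients rests on three conditions: the MDAS is the instrument, baseline is the reference and any fall counts. It uses the documents' r = .82 and an assumed SD of 2-5, and under those conditions the association would be attenuated. The documents do not allow a statement on how many non-responders there would be, and the power figures are illustrations on assumed inputs. The analysis serves a primary objective and the change is easy, so it should be made, but it does not affect the main comparisons of Aims 1 and 2.

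**What to change.** In the Aim 3 logistic regression, make continuous 3-month MDAS change the main predictor of attendance, with baseline MDAS in the model. Repeat with ADIS-5 fear. Report the odds ratio per point or per SD of fall, and check linearity on the log-odds.

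If a responder grouping is wanted, keep it secondary and descriptive. Fix in advance its instrument, baseline as the reference, and a reliable-change cut. With r = .82 that cut would be about 3.5-4.7 MDAS points at an assumed SD of 3-4, to be reset once the trial's own baseline SD is known and before attendance data are examined.

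The cost is a sentence or two in the analysis plan and no new data. The model takes on a linearity assumption, which can be checked. Measurement error in the change score remains, so the fix removes only the loss added by the split.
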